### **8.9.1 *Loss to follow-up***

If a patient is lost to follow-up, every effort should be made to contact the patient's primary physician (GP) to obtain information on the patient's status. Similarly, if a patient's care is transferred to another clinician, every effort should be made so that follow-up information be obtained.

### **8.10 End of trial**

[figure not shown]
The sponsor must notify the main EC of the end of a clinical trial within 90 days of its completion. End of trial is the date of the last visit/data item of the last patient in the trial.

## 9 TRIAL INTERVENTION

### 9.1 Surgical decompression of the peroneal nerve at the fibular head (neurolysis)

Surgical decompression of the peroneal nerve can be performed under local, locoregional or general anaesthesia. Pneumatic compression to restrict blood flow in the operation area during surgery can be used (and will be recorded in the surgery report).

The surgical approach for entrapment at the fibular head is usually through a curvilinear incision just distal to the fibular head. The length of the incision can vary between 3 and 10 centimeters. The subcutaneous tissue is bluntly dissected, and the common peroneal nerve is identified proximal to the peroneus longus muscle. The peroneal nerve is then released from the surrounding fibrous tissue and fascia. The anterior intermuscular septum is usually not cut, but this can be done if deemed necessary. The nerve is decompressed distally as it dives under the peroneus longus muscle. The decompression at this site is essential. Certain authors state that an adequate decompression should extend beyond the bifurcation in the deep and superficial peroneal nerve and should involve cutting the intermuscular septa (1, 114). It is up to the surgeon to decide if decompression beyond the bifurcation is necessary, based on intraoperative findings (recorded in the surgery report). Figure 3 illustrates the incision and decompression at the fibular head.

**Figure 3.** Surgical decompression of the peroneal nerve at the fibular head. *Courtesy of [name].*

The patient will be hospitalized for up to 2 nights or can be operated on in an ambulatory day-care surgery setting. Postoperative treatment follows standard of care and can include physiotherapy and medication, a decision that is left to the treating physician.

A template for reporting the surgical procedure is made and included in appendix 9. All surgeons are advised to use this standardized template, since some technical aspects will be included in the eCRF (length of incision, cutting of the intermuscular septum, decompression beneath the fibular tunnel, decompression beyond the bifurcation, damage to the nerve).

## 9.2 Conservative treatment

Evidence on the conservative management of foot drop is scarce. Willerslev-Olsen et al. (115) found a significant improvement of foot and great toe dorsiflexion in children with cerebral palsy and foot drop after 1 month of gait training. Despite the lack of studies on training to improve foot drop of peripheral origin (as in peroneal neuropathy), a training program is recommended for every patient with foot drop (116). Goals of the treatment are to reduce muscle fiber atrophy, to preserve ankle mobility and to improve gait in general.

A basic standard protocol for physiotherapy is proposed. However, the protocol should be adapted to the clinical presentation and needs of every individual patient. So, if the trial should be mirroring daily practice, some degree of freedom in the conservative treatment should be allowed.

Standard instructions for the physiotherapist will be provided:

- Mobilization of ankle and foot, stretching of the calf muscles (prevention of contractures)
- Tonification of the dorsiflexion- and eversion muscles of the ankle
- Proprioceptive training
- Gait rehabilitation
- Home exercise schedule

Intensity: 60 sessions (F-pathology, Belgium) at a frequency of 1/2 sessions per week, with a possibility of a higher frequency during the first months.

The training program should be progressive. To evaluate the compliance, the patients will be asked to complete a training diary.

We do not advice to use electrostimulation because of the lack of training of younger physiotherapists and the lack of good equipment. The use of electrostimulation is not prohibited. We do not routinely support the use of an orthosis during the first six weeks. Most patients receive a prefabricated orthosis at this stage. However, this does not always meet the requirements of the patients at later stages. When the foot drop is irreversible, an ankle foot orthosis can help to improve everyday mobility.

# 10 SAFETY RECORDING AND REPORTING

## 10.1 Definitions

Term	Definition
Adverse Event (AE)	An AE is any untoward medical occurrence in a patient or subject during an experiment, and which does not necessarily have a causal relationship with this treatment.  An AE can therefore be any unfavorable and unintended sign (including an abnormal laboratory finding), symptom or disease temporally associated with the use of a product, whether or not considered related to the product. Any worsening (i.e., any clinically significant adverse change in the frequency or intensity of a pre-existing condition) should be considered an AE.
Adverse Reaction (AR)	An AR is any untoward and unintended responses to an investigational medicinal product or to an experiment and, when an investigational product is concerned, related to any dose administered.
Serious Adverse Event (SAE)	A serious adverse event is any untoward medical occurrence that: 

• results in death

• is life-threatening

• requires inpatient hospitalisation or prolongation of existing hospitalisation

• results in persistent or significant disability/incapacity

• consists of a congenital anomaly or birth defect

 Other 'important medical events' may also be considered serious if they jeopardise the participant or require an intervention to prevent one of the above consequences.  NOTE: The term "life-threatening" in the definition of "serious" refers to an event in which the participant was at risk of death at the time of the event; it does not refer to an event which hypothetically might have caused death if it were more severe.

*NB: to avoid confusion or misunderstanding of the difference between the terms "serious" and "severe", the following note of clarification is provided: "Severe" is often used to describe intensity of a specific event, which may be of relatively minor medical significance. "Seriousness" is the regulatory definition supplied above.*

## 10.2 Recording of safety findings in function of the available evidence

The participant will be asked to report any adverse event related to the study-specific intervention to the study team. These reported events will be documented by the investigator in the source documents.

The following minimum information should be recorded for each adverse reaction (AR) by the reporting investigator:

- AE description
- Start and stop date of the AR
- Severity
- Seriousness
- Causality assessment to the study interventions

- Outcome

The sponsor will keep detailed records of all AEs reported to him by the investigators and will perform an evaluation with respect to seriousness, causality and expectedness.

A Serious Adverse Event (SAE) is an untoward medical occurrence that results in any of the following:

- Death
- A life-threatening experience
- In patient hospitalisation or prolongation of existing hospitalisation
- A persistent or significant disability or incapacity
- A congenital anomaly or birth defect.

- Important medical events that may be considered an SAE when - based on appropriate medical judgement - they may jeopardise the subject and may require medical or surgical intervention to prevent one of the above outcomes

The term "life threatening" in the definition of SAE refers to an event in which the subject was at risk of death at the time of the event. It does not refer to an event which hypothetically might have caused death if it was more severe.

When reporting adverse events to the sponsor, the investigator will protect confidentiality by excluding the names of individual subjects, personal identification numbers (e.g. social security numbers) or addresses. The unique code number assigned to the trial subject will be used in the report and the investigator retains the code to facilitate data verification by the sponsor and any medical follow-up which may be warranted. The name of the investigator reporting the adverse events will be stated.

After the trial has been completed or terminated, all recorded adverse events will be listed, evaluated and discussed in the final report.

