## 1 BACKGROUND

Peroneal neuropathy is the most common neuropathy in the lower limbs(1-4) and represents the third most common focal neuropathy, after median and ulnar nerve pathology (5, 6). Epidemiologic data on peroneal neuropathy are scarce. Studies from Egypt (7, 8) found a prevalence of symptomatic peroneal neuropathy of 40 per 100.000 inhabitants in a population-based survey, and 19 per 100000 in a community-based study of 42633 subjects. Based on the data from the Egyptian studies (7, 8), 0.6% to 1.2% of all neuropathies are peroneal neuropathies. The reported percentage of 0.6% in the Kandil series is probably an underestimation of the total number of peroneal neuropathies, since all idiopathic neuropathies were reported as a separated category. Cruz-Martinez et al. (9) however, found 150 peroneal neuropathies in a patient database of 1000 neuropathies (15%), contrasting the percentages of Khedr and Kandil. According to Katirji et al.(10), 10% of peroneal neuropathies are bilateral. Motor deficits are frequent and even patients with subclinical peroneal mononeuropathy are at increased risk of falling (11-13). There is no data on the number of subjects with peroneal nerve entrapment suffering from foot drop.

The etiology of peroneal neuropathy is very broad. The nerve can be compressed by cysts and tumors (14), or due to muscle herniation (15). The peroneal nerve is also sensitive to external compression which can result from bracing, wearing a tight cast, habitual crossing of the legs, squatting and kneeling. Peroneal neuropathy is frequently associated with excessive weight loss, as seen after bariatric surgery (3, 16-19) or anorexia nervosa (20); some authors believe that the loss of subcutaneous fat tissue in the area of the fibular head causes increased susceptibility to compression (6, 21). Long-term bedridden patients are also prone to peroneal neuropathy (1, 22, 23). Iatrogenic damage can occur after surgery of the hip, knee and ankle, or even after thoracic-abdominal surgery due to patient positioning. Other potential causes are trauma (23-25) and metabolic disorders (e.g. diabetes mellitus, hypothyroidism) (26).

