## 2 RATIONALE

The rationale for this study is to explore whether a surgical approach to peroneal nerve entrapment is warranted i.e. **does a foot drop, caused by peroneal nerve entrapment, recover faster and better after surgical release?** This question is relevant, given the fact that the actual treatment strategy varies greatly between and even within different centers, depending on the consulting physician.

Since peroneal nerve entrapment represents one of the most common entrapments, and no practice guidelines exist on its preferred treatment, this prospective study will provide important outcome data after conservative treatment (current data very limited), as well as surgical treatment (current data very biased, retrospective in nature and uncontrolled). The impact on quality of life will be assessed and the complications (surgical, chronic pain, sensory changes, ...) of both treatments will be recorded. These data will define future treatment guidelines for this mononeuropathy and is thus relevant for all physicians treating entrapment neuropathies (neurology, neurosurgery, physical medicine, orthopaedic surgery, ...).

There is indeed insufficient data in the available literature to make any recommendations. No studies have compared surgical versus conservative treatment in a prospective manner and currently no guidelines are available. Even data on the prevalence and the spontaneous evolution of peroneal neuropathy are virtually non-existent.

The lack of prospective studies on this topic is remarkable since most patient series on both the conservative and surgical treatment are retrospective in nature. Most patient series are very heterogeneous given the fact that patients with peroneal nerve damage due to different causes were included, which makes it difficult to draw conclusions on the clinical management. Based on the current literature, the percentage of patients with good outcome after conservative treatment varies between 53% and 100% (9, 22, 24, 28, 36-40). Data concerning the spontaneous evolution of peroneal nerve entrapment (without any intervention) is almost absent, except for 15 patients (28, 41). Furthermore, studies discussing prevalence, report contrasting percentages (7-9).

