## 8.7 Trial assessments

In the section below, all study procedures and trial assessments are described, as well as their timing. Several assessments will be performed by the treating physicians, others by the outcome assessor (blinded researcher). The study assessments are listed in the visit and assessment schedule (see Section 8.8).

A list of standard assessments (clinical records, considered daily practice; including motor and sensory function, ability to walk (barefoot), need for orthosis, treatment) will be composed for uniformity across centers. These data will be collected at every study visit and will be recorded in the eCRF. The list of standard assessments is included in appendix 4.

Several questionnaires (EQ-5D 5L, WPAI) will be made available as an online survey (REDCap) for patients. All other questionnaires completed by the subject or proxy are entered into the corresponding eCRF form by the study coordinator. The original paper copies of the questionnaires that are not available online will be filed in the ISF and made available for verification by the site monitor. If patients fail to complete the survey online, the blinded researchers can make sure that the questionnaires are complete during follow-up. If the patient is unable to return to the investigative site for study specific follow-up, the questionnaires will be sent to the patient's home (and the clinical evaluation will be recorded as missing data). Patients will receive a message prior to each evaluation moment, to remind them of the upcoming assessments. At every assessment, the schedule of the assessments to come will be discussed with the patients as an extra reminder.

If visits or data collection time-points are missed, despite previous mentioned efforts, following measures will be taken:

- The outcome assessor will inform the treating physician, PI, clinical trial assistant or any other non-blinded study personnel. The patient will be contacted to reschedule the visit as soon as possible. This cannot be done by the outcome assessor to guarantee blinding.
- If the patient is not able to reschedule, the reason will be documented in the eCRF. If possible, certain assessments will be evaluated through telephone:
  - o EQ-5D 5L questionnaire

- WPAI questionnaire
- Sensory changes
- Ability to walk barefoot
- Need for foot-ankle orthosis
- Return to work
- Registration of treatment

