Suppose the baseline mean 6MWD is 300 meters in the conservative arm and surgical arm of the trial (no difference due to randomization). Mean difference in 6MWD in the surgical arm between baseline and 9 months is 120 meters and mean difference in 6MWD in the conservative arm between baseline and 9 months is 100 meters. Therefore, the difference between both groups is 20 meters. Apart from the assessment of statistical significance, the clinically relevant difference will be defined as the minimum of 10% of the mean minimal predicted age- and sex specific reference value of all patients in the conservative and surgical arm. E.g. assuming an average age of 55 years and 42% of the patients being female(3), the minimal mean predicted 6MWD would be 551.86 meters, resulting in a MCID of 55.2 meters. The actual value applied will be determined by the trial population.

Standardized 6MWT methodology is essential for reproducible and reliable results. The test should be performed in a minimally trafficked area along a flat, straight corridor ideally ≥ 30 meters in length (90, 91). Although the procedural guidelines, formulated in 2002, were made to address patients with respiratory pathology, several items can make the 6MWT in the foot drop trial more standardized:

1. Mark the starting line with brightly colored tape.
2. Mark the length of the hallway every 3m.
3. Mark turn around with a cone.

4. Patients should be wearing comfortable clothing and use their usual walking aids. The use of a foot-ankle orthosis is prohibited.
5. The patient should rest for at least 10 min prior to commencement of testing.
6. Patients should not have exercised vigorously within 2 hours of beginning the test.
7. All patients will be instructed to cover as much distance as possible during six minutes.
8. Subjects will be encouraged every minute. The remaining time will be communicated every minute. An example: When the timer shows 3 minutes remaining, tell the patient the following: "You are doing well. You have only 3 minute left."
9. If the patient stops during testing, the timer should not be stopped. The time at which the patient stopped, and recommenced walking should be noted.
10. Walk distance is measured by counting the number of full laps and rounding to the nearest meter for the partial final lap.

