### Source Documents

ICH E6 1.52, defines source documents as "Original documents, data and records (e.g., hospital records, clinical and office charts, laboratory notes, memoranda, subjects' diaries of evaluation checklists, pharmacy dispensing records, recorded data from automated instruments, copies or transcriptions certified after verification as being accurate and complete, microfiches, photographic negatives, microfilm or magnetic media, x-rays, subject files, and records kept at the pharmacy, at the laboratories, and at medico-technical departments involved in the clinical trial)."

Investigators must keep accurate separate records (other than the eCRFs) of all subjects' visits, being sure to include all pertinent study related information. A statement should be made indicating that the subjects have been enrolled in Protocol and have provided written Informed Consent. Any and all side effects and adverse events must be thoroughly documented. Results of any diagnostic tests conducted during the study should also be included in the source documentation. Telephone conversations with the subjects concerning the study must also be recorded. The Investigator is responsible for maintaining a Subject Identification Log, which will include all subjects who provided informed consent (i.e. to include randomized subjects and screening failures). This confidential subject identification provides the link between named subject source records in the subject file and pseudonymized eCRF data provided to sponsor. The Investigator must retain all study related documentation until at least 25 years after completion of the study. If regional regulations differ, the investigator must retain study related documents by whichever is longer. Study documents should not be destroyed without prior written agreement between the Investigator and sponsor. The sponsor must be notified if the Investigator wishes to assign the study records to another party or move them to another location.

Entries recorded by the subject on the paper copies of the Stanmore questionnaire and functional ambulation categories are considered source data (WPAI, SF-36, EQ-5D 5L and sensory changes will be filled in online through REDCap). Site personnel will review and ensure completeness of the subjects' entries.

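### Section 10.2 asks participants only for intervention-related adverse events, against the protocol's own AE definition, and falls are not collected in either arm

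*Protocol*

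**What the plan says.** Section 10.2 defines what participants are asked: "The participant will be asked to report any adverse event related to the study-specific intervention to the study team". It continues: "These reported events will be documented by the investigator in the source documents". The minimum information to be recorded is set for each adverse reaction, although the list under it mixes AE and AR terms and includes a causality assessment. The sponsor then evaluates seriousness, causality and expectedness again.

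Other sections are wider:

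- Section 10.1 defines an adverse event as an untoward occurrence "which does not necessarily have a causal relationship with this treatment".
- Section 12.1, under Source Documents, says: "Any and all side effects and adverse events must be thoroughly documented".
- The table in 8.8 assigns an AE row and an SAE row to the treating physician, with no relatedness limit.
- Section 2 announces that "the complications (surgical, chronic pain, sensory changes, ...) of both treatments will be recorded".

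Section 3 points the other way and confines safety reporting to what routine care requires.

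On falls, section 1 notes that "even patients with subclinical peroneal mononeuropathy are at increased risk of falling". Section 6 gives fall risk as a reason for referral. Section 2 reports that 16% of interviewed patients saw falling less often as essential to recovery. Section 14.2 counts a lower fall risk as one way to measure better gait.

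**The concern.** A causality judgement belongs to the investigator and the sponsor, after the event is on record. Section 10.2 places a first judgement with the participant, who knows the allocation, and nothing later can recover an event that was never mentioned. Sites cannot follow 10.1, 10.2 and 12.1 together, so practice may differ between them.

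At stake is the harm side of the treatment comparison. Complications and neurological deficits are a listed secondary outcome (4.3.2), and section 2 speaks of both treatments. A wound problem is readily linked to surgery. A fall at home due to a persisting foot drop is less readily linked to physiotherapy, so it may not be reported under the 10.2 wording. There is no data safety monitoring board, partly because patients are expected to signal harm themselves (10.3). The question put to them therefore matters. The primary endpoint is not affected.

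**Working it through.** The point turns on wording, so the main check sets the sections side by side.

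1. **Scope of the question.** 10.1 requires no causal link and 12.1 wants all events. 10.2 asks for related events, and what it says will be documented is the events so reported. The contradiction is direct.
2. **Order of steps.** 10.2 asks investigator and sponsor to assess causality, but only on events that have already passed a relatedness filter. Part of that assessment is pre-empted.
3. **Meaning of the filter.** The Trial Summary lists surgery as the intervention and conservative care as the control. Section 4.1 calls them interventions A and B, and the causality item in 10.2 uses the plural. On the first reading, conservative care has no reportable events at all. On the second, a fall due to the foot drop itself can still be left out.
4. **Structured collection by arm.** 8.7.13 gives ten predefined surgical complications, scored at 10 days and 6 weeks, and 8.8 gives the surgical arm an extra 10-day visit. Conservative care has no matching list.
5. **Falls.** No endpoint in 4.3, no assessment in 8.7, no row in 8.8 and no item in Appendix 4 collects them.
6. **Missed visits.** Section 8.7 says: "If possible, certain assessments will be evaluated through telephone". The list that follows has seven items. Adverse events and surgical complications are not among them.

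**Can a size be derived?** The protocol gives no figure for harms in this trial to reproduce. Its one usable complication figure is the 200-patient retrospective surgical series in section 1: 7 wound problems plus 1 abscess with sepsis. Treating these as separate patients, s = 8/200 = 4%, or 0.04 × 91 = 3.6 patients in the surgical arm.

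Let fS and fC be the fall risks under surgery and conservative care, and c the share of falls recorded, equal in both arms. Assuming that falls and complications are independent:

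- recorded risk, surgery = 1 − (1 − s)(1 − c·fS)
- recorded risk, conservative = c·fC

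With no falls recorded (c = 0) the difference is 4.0 − 0 = +4.0 points (surgery minus conservative), whatever the fall risks. With all falls recorded (c = 1), under **assumed** fall risks:

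| fC / fS (assumed) | Surgery | Conservative | Difference |
|---|---|---|---|
| 5% / 5% | 1 − 0.96 × 0.95 = 8.8% | 5% | +3.8 |
| 10% / 5% | 1 − 0.96 × 0.95 = 8.8% | 10% | −1.2 |
| 20% / 10% | 1 − 0.96 × 0.90 = 13.6% | 20% | −6.4 |
| 30% / 15% | 1 − 0.96 × 0.85 = 18.4% | 30% | −11.6 |

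If falls are equally frequent in both arms, leaving them out hardly changes the comparison (+4.0 against +3.8). If they are more frequent under conservative care, the sign can reverse. The protocol does not say which applies.

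**The case against.** The strongest reply is that 10.2 is not the only route to a record. The table in 8.8 has unrestricted AE and SAE rows, 12.1 wants every event in the source records, section 13 makes SAE documentation a monitoring target, and 10.4 requires all deaths to be reported whatever the cause. A fall leading to admission is an SAE irrespective of cause. Section 3 gives a reason for light safety reporting: both treatments are routine care. A list of surgical complications is one-sided by nature, and harms that both arms can share are scored in both: motor and sensory deficits, pain within the Stanmore score, and EQ-5D-5L.

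Much of this stands, and it rules out two stronger readings.

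- *That falls and other unrelated events go unrecorded, so that the harm comparison is biased against surgery.* The wider sections point to broader recording, and any tilt depends on an excess of falls under conservative care that the protocol does not show.
- *That harm from the study walks has no route to the record and adds to such a tilt.* Section 8.7.5 says of the test: "The use of a foot-ankle orthosis is prohibited". The same item allows usual walking aids, however. The outcome assessor is present, stops during the walk are noted, and the AR definition in 10.1 extends to responses to an experiment. Both arms do the same walks, so a gap there would lose safety information without favouring an arm.

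On the telephone list, 8.7 has the reason for a visit that cannot be rescheduled entered in the eCRF. A complication that the patient gives as the reason would therefore be noted.

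The reply does not remove the contradiction. The rows in 8.8 give no question and no scope, and 12.1 cannot document what nobody was asked about. A routine-care rationale does not explain why 10.1 and 12.1 are wider than 10.2.

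**Conclusion.** The point holds as an internal contradiction with a practical consequence. Followed as written, 10.2 yields harm data filtered by the participant's own attribution, with structured collection in the surgical arm only and no item for falls. Unrelated or disease-related events, especially under conservative care, are not asked for and may be missed.

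The size cannot be stated. The scenarios above rest on assumed fall risks, equal capture in both arms and a complication rate from one retrospective series. They show only that the direction of the recorded difference could depend on whether falls are captured. A reader might infer that the plan is biased against surgery, but the documents do not support that conclusion. The point affects the safety comparison and is cheap to correct, so the change should be made.

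**What to change.** Reconcile sections 3, 8.8, 10.1, 10.2 and 12.1 so that they state one scope for adverse event recording, and say whether the term study-specific intervention covers both arms. Then, in 10.2:

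- Replace the request to participants with a rule of this kind: at each visit common to both arms, an unblinded team member asks every participant the same question about any adverse event since the last contact, whether or not it seems related. Investigator and sponsor judge causality afterwards. The pre-assessment contact described in 8.4 and 8.5 can carry the question without risk to the assessor's blinding.
- Set the minimum data set per adverse event, not per adverse reaction.
- Add one falls item (number since last contact, injury yes/no), reported by arm.

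In 8.7, add adverse events to the list of items that can be collected by telephone.

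The cost is a protocol amendment, one short eCRF form and more minor, unrelated events to enter and list. No treatment or endpoint changes.
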